A Randomized Controlled Trial of PCIT-ED for Preschool Depression

NCT02076425

January 13, 2014

PCIT-ED Study Protocol

Parent Child Interaction Therapy Emotion Development (PCIT-ED) will be conducted with a sample of preschoolers who exhibit symptoms of depression compared to a wait list (WL) control after which participants will receive the active treatment. PCIT-ED is an expansion of PCIT, a well-known, widely used and proven effective treatment for preschool disruptive disorders. To address early disturbances of mood and affect, a novel ED module was added based on empirical data in emotion development. The ED module targets parent emotion learning skills with the goal of training the parent to serve as a more effective emotion teacher and coach to the child. The goal of the ED module is to enhance the child's capacity for emotion recognition and regulation or "emotional competence." In order to test the efficacy of PCIT-ED, to estimate accurate effect sizes and to investigate mediators and moderators of treatment response participants will complete comprehensive pre-, interval, and post-assessments.

SCREENING

Prior to screening potential participants, a research team member will obtain verbal consent (see 'Initial Phone Screen'). Once this is complete and the team member answers parents' questions, the PFC (if not already completed) and then Initial Phone/Exclusion Screen will be administered. If team member suspects possibility of an ASD, the SRS will be administered to the parent. If eligible based on PFC and Initial Phone/Exclusion Screen (and possibly SRS), another phone interview will be scheduled and the team will administer the MDD Phone/Inclusion Screen which will be audio recorded. Research staff will utilize Washington University's Research Electronic Data Capture (REDCap) to administer and record information from potential participants. When potential subjects screen-out based on not meeting MDD eligibility criteria, the research team will send the 'PCIT-ED RCT Screen-Out Follow-Up Letter' to inform them of the possibility of re-screening if the child's moods and behaviors worsen.

BASELINE, POST 1 and POST 2 ASSESSMENTS:

-TAKE HOME:

If eligible based on the MDD Phone Screen, parents will receive several forms (BRIEF, ERC, My Child, Emotion Understanding Parent Questionnaire, BIS/BAS, Contact Information, Teacher Contact Information) in the mail or if families have internet access via REDCap to complete before the laboratory assessment. This will take approximately 1 hour to complete. A copy of the Consent Form and Consent Letter will be included in this take-home packet (sent via mail or email). At the Post 1 & Post 2 assessments, parents will receive this packet/REDCap link (BRIEF, ERC, My Child, Emotion Understanding Parent Questionnaire) prior to the in-office assessment to complete on their own.

-IN-OFFICE:

Parent and child will complete the Parent Child Interaction - DPCIS as well as Teaching Tasks (marble maze, etch-a-sketch, and prohibited toys) at Baseline, Teaching Tasks (magnet puzzle, team drawing and prohibited toys) at Post 1 and Waiting Task at Post 2. The PCI will be video recorded and take approximately 45 minutes to complete.

Then, a research team member will assist the child in completing Handedness, Height & Weight measurement, FACE - Blurry Face & Emotion Labeling, KIDSEDF, Emotion Understanding, KBIT-2, Narratives, Dot Probe task, Narratives for Suicidal Ideation, and Death Interview. All these tasks will be video recorded and take approximately 1.5-2 hours.

The parent will independently complete the BDI, PFC-Scale, ECBI, CBCL, PSI, CCNES, GPSQ, PSDQ, and OC-YC Screener. Another research team member will work with the parent to complete the KSADS-EC, Breastfeeding Questions, LEC-Child, PECFAS/CAFAS, FIGS, HBQ Medical & Peer Relationships sections, Asthma Questionnaire, Religion in Subject Family, and SES measures; this portion will be audio recorded. FIGS will be used to obtain information about the parent reporter; when parents report symptoms or diagnosis of specific disorders, the appropriate screener/checklist will be administered [MDD, Mania, and Anxiety (GAD, OCD, Panic Disorder); Alcohol, Drugs, Psychosis]. Research staff will utilize Washington University's Research Electronic Data Capture (REDCap) to administer and record information from parent participants. Parents will complete the MSCEIT online via a secure website. They will also complete the Parent-Child Conflict Tactics Scales and the Parental Survey of Media Exposure or Media Quotient - A Questionnaire for Parents via REDCap survey. The parent assessment will take approximately 4-5 hours. Clinicians will complete the CGAS following the assessment. Any self-report measures not completed in office may be completed via REDCap or paper copies at home.

-TEACHER:

We will also ask parents to give permission to contact their child's teacher to complete a questionnaire regarding his/her behaviors and development. Teachers will receive the C-TRF/TRF in the mail or a REDCap link via email with a copy of the permission letter and brief description of the study/measure to be completed and returned via mail/electronically via REDCap.

After completing the Baseline assessment, if the participant child continues to meet DSM MDD criteria (adjusted for development) families will be randomly assigned to receive immediate treatment or be placed on an 18-week wait list after which they will receive treatment.

TREATMENT (Immediate Treatment Randomization: ~Week 1-18 or Wait List Randomization: ~Week 18-36) During the treatment, parent and child will work with a therapist at the Early Emotional Development Program each week for 18 weeks. Each session will last approximately 1 hour, although there are a few weeks when sessions will last approximately 1.5-2 hours. During these sessions, parent and child will work with a therapist to improve their relationship, learn safe and effective disciplinary techniques, as well as both learn strategies to deal with a range of emotions. (See attached Sessions Manual) The therapist will assign homework and activities on a weekly basis. Parents will complete the ECBI prior to each session. Therapists will complete the DPICS, EDCI, TIC, OC-YC Screener, and Acceptance Inventory throughout the course of treatment.

INTERVAL A, B, C & D ASSESSMENTS (~ Weeks 6, 12, 24, 30) Either over the phone, at the Early Emotional Development Program, or via REDCap, parents will complete the HBQ-P Peer & Medication section, CBCL, PFC-Scale, BDI, PSI, CCNES and TAI. This will take approximately 1-1.5 hours to complete.

DISCONTINUATION

If at any point in the study the family decides to discontinue their participation, the research team will ask the parent to complete an Exit Questionnaire and potentially the parent and child to complete the Post 1 or Post 2 assessment if families are willing to do so.

LONG TERM FOLLOW UP

After the completion of planned study visits (Baseline, Post 1, and Post 2 assessments), the research team will contact families via phone and/or email with the contact information they provided us. This will be done in order to ensure up-to-date contact information. The research team will update their contact information in the REDCap database for future follow-up studies with this population. Participants can let us know if they would no longer like to be contacted for future studies and we will note that in the REDCap database and cease contact.

PCIT-ED Statistical Analysis Plan

All measures will be collected at pre- and post-treatment assessments (except EI). In addition, the HBQ-P (measuring symptom severity of all Axis I disorders and impairment), PFC-Scale, parent BDI-II, PSI, EDCI (measuring ESL in both groups) and will be collected at the 6- and 12-week assessments in both groups. In the PCIT-ED group, these interval assessments correspond to completion of the CDI and PDI modules.

An intent-to-treat analytic approach will be employed. Multiple imputation will be utilized for subjects who discontinue during the study and do not complete the post-treatment assessment. Multiple imputation is desirable because instead of filling in a single value for each missing data point, each missing value is replaced with a set of plausible values, creating multiple imputed datasets. These datasets are then analyzed using standard procedures (that would be appropriate for a single, complete dataset), and results from the multiple data sets are combined into one set of results. The SAS procedures MI and MIANALYZE will be used for creating and analyzing multiple imputed data, resulting in statistically valid results that appropriately reflect the uncertainty due to missing values.

Multiple imputation is a useful method for analysis of datasets with data that are plausibly missing at random (MAR). Missing values rarely occur completely at random (MCAR). Instead, missing values are typically based on other variables, so they are MAR. During the multiple imputation process, the analyst should use all observed variables available in predicting missing values (even variables not used in analysis). If these variables are useful for predicting missing values, the multiple imputation increases power. Furthermore, by using an exhaustive set of predictor variables, the multiple imputation process creates a largely MAR dataset. Thus, multiple imputation can convert missing not at random (MNAR) data to MAR.

Simulation was used to determine sample size needed for analyzing multiple imputed datasets. We assume N=90 completers in each group, so a simulated dataset with N=180 subjects was created. Change in PAPA MDD severity sum scores were generated assuming normally distributed scores with a SD of 4.69 (pooled SD from our pilot RCT) and a mean difference in change scores in the two groups of 2.5. The demographic variables gender, age, race, family income, parental education level, and parental marital status were also included in this dataset. To simulate demographic characteristics, complete demographic profiles from the subjects in our pilot RCT were drawn with replacement 180 times and randomly assigned to the 180 simulated cases. A general linear model of change in PAPA MDD severity sum score by group was conducted for this simulated dataset.

To address differential dropout and its impact on power, we assume a 25% drop-out rate in the PCIT-ED group and a 30% drop-out rate in the WL group. So 25% and 30% of the simulated PCIT-ED and WL subjects' MDD severity sum change scores were set to missing, respectively, using a random number generator. Because the simulated missingness was random, missing values are not predicted by anything, so data are missing completely at random (MCAR). This should be realistic for the multiple imputation power analysis that follows.

The SAS v9.2 MI procedure was used to create multiple imputed datasets with MDD severity sum change scores based on the simulated demographic variables in the dataset. Multiple imputation was conducted 10 times, with 10 imputed datasets created. The SAS v9.2 MIANALYZE procedure was then used to run a general linear model of change scores by group for each set of multiple imputed datasets. Table 5 shows the results of the general linear model in the complete simulated dataset and then each of the 10 multiple imputed datasets.

Dataset	Estimate	SE	SE ²	t	p
Complete Simulated Dataset	-2.278	0.729	0.532	-3.12	0.0021
Multiple Imputed Dataset 1	-2.307	0.745	0.555	-3.10	0.0020
Multiple Imputed Dataset 2	-1.951	0.855	0.731	-2.28	0.0241
Multiple Imputed Dataset 3	-2.090	0.569	0.756	-2.40	0.0182
Multiple Imputed Dataset 4	-2.121	0.848	0.718	-2.50	0.0137
Multiple Imputed Dataset 5	-2.063	0.816	0.666	-2.53	0.0122
Multiple Imputed Dataset 6	-1.894	0.796	0.633	-2.38	0.0178
Multiple Imputed Dataset 7	-2.220	0.824	0.679	-2.69	0.0078
Multiple Imputed Dataset 8	-2.079	0.846	0.715	-2.46	0.0152
Multiple Imputed Dataset 9	-2.121	0.850	0.723	-2.49	0.0141
Multiple Imputed Dataset 10	-2.124	0.845	0.714	-2.51	0.0128
Mean	-2.097		0.689		
Variance	0.014				

Rubin's method for determining the uncertainty of the imputed estimate was employed. Following this method, the total variance from the imputed datasets is $T = (\text{mean within-imputation variance}) + (1 + 1/(N \text{ sets of imputed datasets})) * (\text{between-imputations variance})$

= $0.689 + 1.1 * 0.014 = 0.704$. The SE^2 of the model conducted on the complete simulated dataset is 0.532. The ratio of these two values is $0.704/0.532 = 0.32$.

So, the relative increase in variance due to missing values is 32%, indicating that $1.32 * 180$ subjects = 238 subjects are required to attain the same power that would be attained in a sample of 180 subjects who all complete the study. In other words, 238 subjects must be enrolled in the study, with 180 completing, to achieve the same power when using multiple imputation as would be achieved if 180 subjects were enrolled and all completed. If multiple imputation were not used, and only complete cases were analyzed, approximately 238 subjects would have to be enrolled to produce 180 complete cases. Thus, multiple imputation is more efficient than complete-case analysis, in addition to avoiding bias due to MAR missingness.

A secondary analytic approach will be to use mixed models on non-imputed data. Mixed models can be used to analyze repeated measures data without discarding subjects with missing data. Mixed models will be used for measures only obtained at pre- and post-assessment and on measures with interval assessments. Analytic approaches for each set of specific aims and hypotheses are detailed below.

Specific Aim 1: To conduct an RCT of an early dyadic intervention for PO-MDD, PCIT-ED, compared to a WL control condition.

Hypothesis 1A: Compared to those randomized to the WL, preschoolers who are first randomized to PCIT-ED will show significantly increased rates of remission, greater reductions in MDD symptoms, and decreases in impairment.

Hypothesis 1B: Compared to those randomized to the WL, preschoolers who are first randomized to PCIT-ED will show significantly greater increases in emotional competence measured by the ability to accurately identify emotions in themselves and others and the ability to effectively regulate intense emotions.

Hypothesis 1C: Compared to those on the WL, parents who are first randomized to PCIT-ED will show significantly greater increases in emotion skill learning (ESL) and reductions in MDD symptoms and parenting stress.

Analytic Approach: Continuous post-assessment scores will be compared between PCIT-ED and WL groups using analysis of covariance, covarying for pre-assessment scores. The stratification variables, gender and externalizing comorbid diagnoses, will also be included as covariates in the models.

PFC-Scale and PAPA MDD severity sum scores will be used to assess differences in depressive symptoms; HBQ and PAPA impairment scores will be analyzed to determine differences in functional impairment. Differences in emotion regulation (as an executive function) in the two groups will be examined using scores from the BRIEF-P; emotion development will be analyzed using scores from the ERC, Emotion Understanding, FACE, KIDSEDF, and the "Waiting" and "Puzzle" tasks. Post-assessment EDCl, BDI-II, and PSI scores will be compared between PCIT-ED and WL groups to determine differences in increases in Emotion Skill Learning and reduction of parental depressive symptoms and parenting stress.

Rates of remission (defined by 50% reduction in MDD severity and not meeting diagnostic criteria) will be compared in the PCIT-ED and WL subjects using logistic regression.

Interval assessment scores will also be analyzed across PCIT-ED and WL groups in repeated measures mixed models. In these models, repeated measures of PFC-Scale, HBQ MDD and externalizing co-morbidity severity and impairment, PSI and ESL (measured by EDCl) at pre-assessment, 6-week assessment, 12-week assessment, and post-assessment will be compared between the PCIT-ED and WL groups.

In addition to the analyses described above, pre-assessment variables that could possibly be associated with outcome, such as subject age and maternal depression, will be investigated as potential predictors of outcome.

Specific Aim 2: To investigate mediators and moderators of treatment effects.

Hypothesis 2A: Parental emotion skill learning (ESL) will mediate treatment effects. Child depression outcomes will be mediated by parental ESL.

Hypothesis 2B: Parental Emotional Intelligence (EI, a stable trait measured at baseline by MSCEIT) will be a moderator of ESL and child outcome. Parents with higher EI will show better ESL, and as a result, children of parents with high EI will show better outcomes than children of parents with low EI.

Analytic Approach: Parental ESL will be measured with the Emotion Development Coding instrument. This is an itemized assessment of parents' emotion skill learning. Each item is rated as 3=satisfactory, 2=needs practice, or 1=not evident. The total ESL score will be calculated as the mean of these items.

To assess parental ESL as a potential mediator of the relationship between treatment group and child treatment response, a macro (for SAS or SPSS) developed by Hayes will be utilized. For mediation analyses, the PROCESS macro estimates path coefficients in a mediation model and generates bootstrap confidence intervals for the indirect effects of the independent variable on the dependent variable through a mediator variable. It is also possible to include covariates not proposed to be mediators in the model. Paternal ESL will be evaluated by entering post ESL score into the model as a potential mediator, with treatment group as the independent variable and change in PAPA MDD severity sum score as the dependent variable.

Power for Mediation: To estimate power for this mediation analysis, the following steps were taken. First, we expect the difference in MDD severity sum change score in the two groups to be approximately 2.5, with a SD of 4.69 (based on our pilot study). With 90 subjects per group, an alpha of 0.05, and a 1-sided test, power=0.97. Next, we expect the correlation of change in MDD severity sum score and ESL score to be approximately 0.25. Using Fisher's Z transformation with a sample size of 180, the correlation of 0.25 transforms to $Z = \tanh(0.25) * \sqrt{180-3} = 3.398$. Subtracting 1.96 gives 1.438, corresponding to power=0.92. Thus, we will be well-powered to detect a mediation effect.

To assess parental emotional intelligence (EI) as a potential moderator of treatment response, the PROCESS macro will be used. For moderation analyses, the PROCESS macro

estimates a moderation model with the effect of the independent variable on the dependent variable moderated by a proposed moderator variable. The independent variable (ESL score) and proposed moderator variable (pre-assessment parental EI) are centered to eliminate any multicollinearity effects. The macro generates the conditional effects of ESL score on the dependent variable (MDD severity sum score) at values of EI score equal to selected percentiles (e.g., 10th, 25th, 50th, 75th, and 90th percentiles) of the distribution in the sample. The Johnson-Neyman technique will be used to identify the values of EI score at which point the effect of ESL score changes from statistically significant to statistically non-significant. If EI score is found to be a significant moderator, the independent and moderator variables (ESL score and pre-assessment EI score) will be dichotomized so that all subjects fall into 1 of 4 categories (low ESL with low parental EI, low ESL with high parental EI, high ESL with low parental EI, and high ESL with high parental EI). Post-hoc pair-wise comparisons of treatment outcome in these 4 groups will be conducted.

Power for Moderation: To estimate power for this moderation analysis, a simulated dataset of 90 PCIT-ED subjects was created. This dataset contained variables for parental ESL, parental EI, and change in MDD severity sum score. Random data was generated for 45 “high EI” subjects and 45 “low EI” subjects assuming normally distributed data for each of these variables, with SD’s based on our pilot study (SD=0.22 for ESL, SD=15.6 for EI, SD=4.69 for MDD change score). The mean scores for the random normally distributed data varied in the two groups as we expect it to in the proposed study. For the “high EI” group, assumed means were 2.1 for ESL, 118 for EI, and -6.5 for MDD change. For the “low EI” group, assumed means were 2.5 for ESL, 99 for EI, and -1 for MDD change. Running the PROCESS macro on the simulated dataset yielded a significant interaction of ESL and EI, with a coefficient=0.2440 and SE=0.0758. Subtracting 1.96 from the corresponding t score (3.219) gave Z=1.259, which corresponds to power=0.90.

Specific Aim 3: To investigate whether reductions in depressive symptom severity and diagnostic remission is sustained 18 weeks after treatment has ended in those randomized to PCIT-ED first.

Hypothesis 3: MDD remission (not meeting diagnostic criteria for ≥ 2 weeks) will be sustained at the 18 week follow-up in 80% of subjects who were in remission at the post-treatment assessment.

Analytic Approach: Rate of 18 week remission in subjects who met remission requirements at the post assessment will be calculated and compared to the 80% expected rate using a Chi-square goodness-of-fit test.

General Data Analysis Considerations: All outcome measures other than MDD diagnosis are continuous. The PFC-Scale and MDD severity scores from our pilot PCIT-ED and DEPI subjects were approximately normally distributed, as determined by the Shapiro-Wilk test. However, if these scores or other outcome scores are found to be from non-normal distributions, the data will be log- or power-transformed prior to analysis. Bonferroni correction will be used to limit the possibility of Type I errors for the main outcomes. A less conservative correction, such as the Bonferroni-Holm correction, will be applied for tests of other outcomes.

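### The SAP's one worked imputation names demographics but not treatment arm; omitting arm would shrink the effect by about 27–28%, and 238 enrolled would not give the stated power

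*Combined protocol and SAP*

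**What the plan says.** The Statistical Analysis Plan adopts an intent-to-treat approach: "Multiple imputation will be utilized for subjects who discontinue during the study and do not complete the post-treatment assessment".

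Two places bear on what goes into the imputation model.

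- **General advice, before the sample-size simulation.** "the analyst should use all observed variables available in predicting missing values (even variables not used in analysis". The same paragraph adds that "by using an exhaustive set of predictor variables, the multiple imputation process creates a largely MAR dataset". No variable is named.
- **The sample-size simulation.** The setup is "We assume N=90 completers in each group, so a simulated dataset with N=180 subjects was created". On covariates, "The demographic variables gender, age, race, family income, parental education level, and parental marital status were also included in this dataset"; their profiles were "drawn with replacement 180 times and randomly assigned to the 180 simulated cases". PROC MI was then used to impute "MDD severity sum change scores based on the simulated demographic variables in the dataset". Group appears only in the next step, the linear model fitted after imputation.

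From Table 5 the SAP derives a 32% increase in variance. It concludes that 238 enrolled, analysed with multiple imputation, have the power of 180 subjects who all complete.

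**The concern.** An imputation model should contain every term of the analysis model, above all the treatment indicator. If arm is left out, a missing outcome in either arm is filled from the pooled distribution of both. The imputed cases then carry no treatment difference and the estimate is pulled toward zero. This happens even when data are missing completely at random, where a complete-case comparison would be unbiased. Imputation would then introduce a bias that the SAP adopts it to avoid.

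In the simulation the demographics cannot stand in for arm, because they were assigned to cases at random and so carry no information on arm or outcome.

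Two things are at stake. A programmer who follows the worked example would leave arm out of the main analysis, and one who follows the general advice would put it in; the SAP permits both. And if the planning simulation omitted arm, variance inflation alone does not measure the power lost, because the effect shrinks as well.

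**Working it through.** **Inputs** (SAP, sample-size simulation): 90 per arm, difference 2.5, SD 4.69 (variance 21.996), dropout 25% in PCIT-ED and 30% in WL, missing completely at random, 10 imputations, change score analysed by group. Assumption: the 238 are split equally, 119 per arm, as in the simulation.

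**1. The plan's own figure.** The Table 5 rows give mean SE² 0.689 and variance of the estimates 0.0139. T = 0.689 + 1.1 × 0.0139 = 0.704. T/0.532 = 1.32 (the text prints 0.32, which is the excess over 1). 1.32 × 180 = 237.6, rounded to 238. This reproduces. Power with 90 complete per arm is 0.97 one-sided, as stated under Power for Mediation, and 0.95 two-sided.

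**2. Shrinkage if arm is omitted.** Let d1 = 0.25, d0 = 0.30, and let m be the PCIT-ED share of observed cases: m = 67.5/(67.5 + 63) = 0.517. Each missing value has as its expectation the pooled observed mean, so the imputed difference is k times the observed-case difference:

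k = (1 − d1) + (d1 − d0) × m = 0.75 − 0.05 × 0.517 = 0.724

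2.5 × 0.724 = 1.81, a shrinkage of 27.6%. A simulation (4,000 trials per model, six uninformative covariates, Rubin pooling) gave 27.7% with arm omitted and 0.8% with arm included, the latter within Monte Carlo error. With equal dropout the shrinkage equals the dropout rate: 10%, 20% or 30%.

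**3. Two-sided power at 119 per arm.** Simulation gives about 0.77 with arm omitted and about 0.92 with arm included. A hand check uses the mean simulated total variances at 90 per arm (0.691 and 0.725), scaled by 90/119. Observed cases are 89.25 and 83.3, so the observed-case variance is 21.996 × (1/89.25 + 1/83.3) = 0.5105.

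- Omitted: threshold 1.96 × √(0.691 × 90/119) = 1.417. Between-imputation variance is 21.996 × (29.75 + 35.7)/119² = 0.1017. The estimate's variance is 0.724² × 0.5105 + 0.1017/10 = 0.278, SD 0.527. (1.81 − 1.417)/0.527 = 0.75, power about 0.77.
- Included: threshold 1.96 × √(0.725 × 90/119) = 1.451. Between-imputation variance is 0.1017 + 21.996 × (0.25²/89.25 + 0.30²/83.3) = 0.141. The estimate's variance is 0.5105 + 0.141/10 = 0.525, SD 0.724. (2.5 − 1.451)/0.724 = 1.45, power about 0.93.

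**4. Variance inflation.** The simulated mean ratio of imputed to complete-data variance is about 1.4 with arm omitted (1.39 and 1.41 in two runs) and 1.47 with arm included. The SAP's 1.32, from one dataset, is below both.

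**5. What Table 5 shows about the model used.** Two signals conflict.

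- *Variance ratio.* Treat each row as a pooled result from 10 imputations. Its t and p imply degrees of freedom 9 × (1 + 1/r)², where r = 1.1 × between/within variance. Row 2, for example (t = −2.28, p = 0.0241), implies about 142, so r is about 0.34. The mean over rows is 0.305, reading the SE in row 3 as 0.869 to match its SE². The simulated expectation is 0.32 to 0.33 with arm omitted and 0.43 with arm included; a mean of 0.305 or less arises in about 37% and 2 to 3% of datasets respectively. This leans toward omission.
- *Point estimates.* Attenuation is 1 − 2.097/2.278 = 7.9%. With a full-data effect near −2.278, attenuation that small or smaller arises in about 10% of trials with arm omitted and 65% with arm included. Omission would need an observed-case effect of −2.097/0.724 = −2.90, which is 1.37 SD from −2.278 (two-sided p about 0.17). This leans toward inclusion.

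**The case against.** The strongest reply is that the general advice already answers the point. Randomised arm is observed for everyone and is the main analysis variable, so a rule to use all observed variables plainly reaches it, along with baseline and interval scores. The sentence about demographics is a past-tense account of a planning exercise on synthetic data that had no baseline or interval scores, and nothing says it will be the template for the trial. Nor does it say that arm was left out. All of this stands. A reader might infer that the trial's main analysis will be biased by 27%; the documents do not support that, because omission is an inference from silence.

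A reader might also take Table 5 as proof that arm was omitted. It is one synthetic dataset, the ratio is recovered from rounded p-values (single rows range from 0.09 to 0.46), and the point estimates lean the other way.

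A third tempting reading is that 238 is merely an artefact of a mis-specified imputation. That goes too far. Even with arm omitted the expected inflation is about 1.4, so omission explains only part of the low 1.32, and the rest is compatible with chance. The SAP also quotes about 238 for a complete-case analysis, so the number does not hang on this model alone.

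Finally, the secondary mixed models on non-imputed data would not inherit the bias and could expose a discrepancy. That limits the harm but does not remove the ambiguity in the main analysis.

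**Conclusion.** The concern holds as a conditional one. The SAP does not list the predictors of its imputation model or name arm among them, and its only worked example names demographics alone. If arm were omitted, the expected effect would fall by about 27–28% at 25%/30% dropout. Two-sided power at 119 per arm would be about 0.77 rather than about 0.92, against 0.95 for 180 completers, so the claimed equivalence of 238 enrolled and 180 completing would not hold.

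These figures assume the SAP's difference and SD, data missing completely at random, equal allocation, and covariates that predict neither arm nor outcome. In the trial, 6- and 12-week scores in the model would carry some of the treatment difference, so shrinkage could be smaller even without arm. Power computed at 90 randomised per arm (about 0.62 omitted, 0.83 included) is not the relevant comparison, because the SAP enrols 238. Table 5 does not settle which model was used.

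**What to change.** State in the SAP that the imputation model includes treatment arm, or that imputation is done separately by arm (a BY statement in PROC MI). List the other predictors: baseline score, the stratification variables, the 6- and 12-week scores and the demographics.

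Re-run the Table 5 simulation with arm in the model, over many simulated datasets rather than one. Restate the variance inflation, which should come out at about 1.4 to 1.5 rather than 1.32, and report the power that 238 enrolled delivers.

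The cost is a sentence or two of text and a re-run of existing code, with no new data. The downside is a slightly less favourable stated figure. If arm was always intended, saying so costs nothing.
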